## **13.6 Analysis of the Primary Objectives**

### **13.6.1 Primary Efficacy Variable**

The primary variable is the change from baseline in UCT score. This variable will be summarized using descriptive statistics of mean, median, minimum, and maximum at Weeks 4, 8, 12, 16, 20, 24, and 28. A 95% confidence interval for the mean will be computed. The summaries will be provided for all 3 cohorts combined as well as for each individual cohort.

Additionally, subjects achieving complete response (CR: defined as the total UCT score = 16) will be summarized with number and percent of subjects for each visit. Subjects achieving 0, 1, 2, 3, and 4 CRs over the 7 post-baseline visits will also be summarized. Refer to the SAP for additional information.

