#### 10.4.2 Urticaria Control Test

The urticarial control test (UCT) is an instrument that is valid in all types of chronic urticaria, not only for CSU, and it can also be used in urticaria subjects suffering from recurrent angioedema. The UCT is a 4-item questionnaire for assessing CU disease activity retrospectively over the previous 4 weeks. Each item is rated on a Likert-type scale (0 = very often to 4 = not at all) and a total score is calculated (range, 0 to 16; higher scores indicate better disease control; scores  $\geq 12$  are consistent with well-controlled disease. The higher the achieved score, the higher the level of disease control.

UCT complete response is defined as a score of 16. Clinically relevant response is defined as improvement of 3 or more points in the UCT score (minimal clinically important difference [MCID]). The UCT total score will not be calculated when  $>1$  item within the questionnaire is missing.

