3.7 Changes to Analyses Planned in the Protocol

None.

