UCT Response (all CU subjects)	UCT score ranges from 0 to 16. CR is UCT score ≥ 12 AND an increase from baseline in UCT score of ≥ 3 points. CMR is an increase in UCT score of ≥ 3 points. DC is UCT score ≥ 12 . An increase from baseline in UCT score of ≥ 3 points is also regarded as the minimally clinically important difference.
UAS7 Response (CSU subjects)	Weekly UAS7 ranges from 0 to 42. [REDACTED]
[REDACTED] Response (CholU subjects)	Weekly [REDACTED] score ranges from 0 to 168. [REDACTED]

5. Efficacy and Safety Variables

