5.2 Secondary Endpoints

- 1) Proportion of subjects with CR, CMR, and DC based on UCT (all patients) at all time points. Section 4 provides the definition of CR, CMR, and DC.
- 2) Change from baseline in disease activity as assessed by UAS7 at each week in CSU patients. If Week 10 or Week 22 measures are not available, they will be imputed with the last non-missing weekly UAS7 (LOCF). The data summary will include Week 10 and Week 22 derived from the available data and Week 10/LOCF and Week 22/LOCF from the available plus the imputed data.

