7.7.1.3 Secondary Efficacy Analyses

All summaries will be provided for each cohort.

- 1) Subjects achieving UCT CR and CMR will be tabulated with % of subjects for each visit. Subjects achieving a maximum of 0, 1, 2, 3, or 4 responses over the 8 post-baseline visits (subjects enrolled under Protocol Amendment 3) will also be tabulated. A 95% CI for the % responses will be calculated using the binomial distribution. Subjects achieving UCT DC will be similarly summarized.
- 2) Changes from baseline in UAS7 in CSU patients will be summarized similarly for each week the diary is collected. A 95% CI for the mean change will be reported. This analysis will also be carried out in the subgroup of CSU-XN patients with baseline UAS7 ≥ 16 .

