11.12 Appendix C: List of Tables, Listings, and Figures

Table No.	Title	Population

Listing No.	Title	Population

Figure No.	Title	Population

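### The SAP gives 'complete response' to UCT 12 or more with a 3-point gain, plans no readable UCT = 16 table as the protocol requires, and declares no change from the protocol

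*Protocol*

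**What the plan says.** **Protocol, outcome and analysis sections.** Section 10.4.2 states that "UCT complete response is defined as a score of 16". Section 13.6.1 repeats the definition and plans the table: "complete response (CR: defined as the total UCT score = 16) will be summarized with number and percent of subjects for each visit".

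**Protocol, extended-dosing passages.** Seven places attach the words Complete Response to a Week 22 UCT of 12 or more: Synopsis inclusion criterion 10, Section 6.1.4, Section 7.2.1 criterion 10, Section 8.3.5, Table 3 note t, and the Summary and Entry Criteria of Appendix 2. SAP 3.2.1 repeats this use.

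**SAP.** The UCT Response row of the definitions table in Section 4 reads "CR is UCT score ≥ 12 AND an increase from baseline in UCT score", and the required increase is at least 3 points. The same row defines CMR as a gain of at least 3 points and DC as a score of 12 or more. Section 5.2 lists as a secondary endpoint the "Proportion of subjects with CR, CMR, and DC based on UCT (all patients) at all time points". Section 7.7.1.3 says "Subjects achieving UCT CR and CMR will be tabulated with % of subjects for each visit", with DC handled in the same way. Under Section 3.7, "Changes to Analyses Planned in the Protocol", the whole entry is the word None.

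Both documents give the SAP precedence where they differ (Protocol 13, SAP 1).

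**The concern.** The precedence clauses settle which rule the programmer applies. They do not make the None in SAP 3.7 true. A responder outcome that the protocol's analysis section defines and schedules by visit has been replaced, under the same name, by an easier one. The stricter rate is not planned in any readable part of the SAP.

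The SAP's own description of the questionnaire (Appendix B.2) reserves complete control for 16 points and calls 12 or more well controlled. The reported complete response rate can therefore include patients whom the instrument would call only well controlled. Anyone comparing protocol with report would find one label, two meanings and no declared change. In an open-label study with no control group and no hypothesis tests, descriptive responder rates are among the results readers look at most, so the label matters.

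**Working it through.** The documents state no response rate or sample-size figure that depends on this definition, so there is nothing to reproduce. The check compares the rules and then counts the possible scores.

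**Rules compared**

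| Source | Label | Rule |
|---|---|---|
| Protocol 10.4.2, 13.6.1 | Complete response | UCT = 16 |
| Protocol extended-dosing passages, SAP 3.2.1 | Complete Response | Week 22 UCT ≥ 12 (with baseline ≤ 5 as a further criterion) |
| SAP Section 4 | CR | UCT ≥ 12 and gain ≥ 3 |

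**Inputs**

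- The UCT ranges from 0 to 16 (Protocol 10.4.2, SAP Section 4).
- Entry requires UCT below 12 at enrollment (Protocol 7.2.1, criterion 9), and enrollment is the first dose (Protocol 6.1.1). An eligible baseline is therefore 0 to 11.
- Each cohort has about 12 subjects (Protocol 7, SAP 3.3).

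**Direction.** The smallest gain that reaches 16 from an eligible baseline is 16 − 11 = 5, which exceeds 3. Every UCT = 16 is therefore also a SAP CR, and the SAP rate cannot be the lower of the two.

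**Possible score pairs, all eligible baselines**

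- Baselines 0 to 11 with visit scores 12 to 16: 12 × 5 = 60 pairs.
- Pairs failing the 3-point gain: (10, 12), (11, 12) and (11, 13), so 3.
- SAP CR: 60 − 3 = 57.
- UCT = 16: 12, one for each baseline.
- SAP CR but not 16: 57 − 12 = 45.

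**Possible score pairs, extended-dosing criteria**

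- Baselines 0 to 5 with Week 22 scores 12 to 16: 6 × 5 = 30 pairs.
- The smallest gain is 12 − 5 = 7, so all 30 are SAP CR.
- UCT = 16: 6. Not 16: 30 − 6 = 24.

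These are possible combinations of scores. They are not subjects and not expected frequencies.

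**Effect on a reported rate.** In a cohort of 12 with all scores available, one subject is 1/12 = 8.3 percentage points. Each SAP CR subject scoring 12 to 15 raises the SAP rate by that amount and leaves the UCT = 16 rate unchanged. A SAP CR count of *k* is compatible with any UCT = 16 count from 0 to *k*.

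**Response tally (minor).** SAP 7.7.1.3 also plans "Subjects achieving a maximum of 0, 1, 2, 3, or 4 responses over the 8 post-baseline visits" for Amendment 3 subjects. SAP 7.7.1 lists Weeks 4, 8, 12, 16, 20, 22, 24 and 28, which is 8 visits. On a plain reading, 5 to 8 responses have no category, although the word maximum is unclear there. Protocol 13.6.1 has the same cut-off at 4 over 7 visits, so the SAP inherited it.

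**The case against.** The strongest reply is that this is a labelling matter. The outcome is secondary and descriptive, the SAP states its definition in full, and the SAP takes precedence, so the analyst has one clear rule. The mean change in UCT is untouched, and SAP 6.1 promises subject listings from which a UCT = 16 rate can be recovered. All of this stands, and it limits the weight of the point. It does not correct SAP 3.7 or put the planned rate in the report.

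A second reply is that Protocol 13.6.1 may be the outdated text. It speaks of 3 cohorts where four are listed, and it omits Week 22, the primary time point. The SAP is based on Amendment 4/4.1, and the extended-dosing passages added by Amendment 4.1 use the 12-or-more sense. The documents do not say which sense was intended. That is a reason to reconcile the label and declare the choice. It does not support an entry of None.

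Two qualifications also stand:

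- The one-directional result needs an eligible baseline. A subject enrolled in breach of the entry criterion with a baseline of 14 to 16 and a later score of 16 would meet UCT = 16 but not SAP CR.
- SAP Appendix C, "List of Tables, Listings, and Figures", and Appendix D, the table shells, have no readable content in this copy. A UCT = 16 row in a shell cannot be excluded. Even so, the changed definition and the None entry would remain.

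**Conclusion.** The point holds. The SAP replaces the protocol's analysis definition of UCT complete response with a looser one, plans no UCT = 16 rate in its readable text, and declares no change. The protocol contributes by using the label in two senses; the SAP's CR is close to the extended-dosing sense but is not the one in the protocol's analysis section.

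For eligible baselines the reported rate is equal to or higher than the planned one, by 8.3 percentage points per affected subject in a fully observed cohort of 12. The total difference cannot be estimated because the documents give no score distribution. The primary analysis is unaffected and no data are lost. The SAP should be corrected, but the point does not threaten the study's main result.

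**What to change.** - **SAP 5.2 and 7.7.1.3:** add the number and percent with UCT = 16 by cohort and visit, as Protocol 13.6.1 plans, or state why this is dropped.
- **SAP Section 4:** give the outcome of 12 or more with a 3-point gain a name other than complete response.
- **SAP 3.7:** replace None with an entry that records the change of definition and notes the protocol's two senses of the label. Check the rest of the entry at the same time: the Week 10 time point for Amendment 2.1 subjects and the LOCF imputation in SAP 5.1 are also absent from Protocol 5.1 and 13.6.1.
- **Protocol and SAP 3.2.1:** reconcile the label between Protocol 10.4.2 and 13.6.1 on one side and the seven extended-dosing passages and SAP 3.2.1 on the other, without changing any entry criterion.
- **Minor:** tabulate the response count as 0 to 8 for Amendment 3 subjects.

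The SAP cost is wording edits and one extra row per UCT responder table, from data already collected. The protocol wording goes through the amendment process (Protocol 15.1) and can wait for the next amendment if SAP 3.7 records the two senses. For eligible subjects, the rate called complete would be equal to or less favourable than the current SAP rate.

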## **13.7 Analysis of Secondary Objectives**

### **13.7.1 Secondary Efficacy Variables**

The [REDACTED], and weekly number of symptom-free days will be summarized analogous to the primary endpoint, as a mean difference from Baseline (Visit 1) to weeks 4, 8, 12, 16, 20, 22, 24, and 28.

Number and percent of subjects receiving rescue medication will be summarized.

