#### 4.2 Secondary Objectives

The effect of AK002 on urticaria symptoms, QOL, provocation testing, and histological criteria

The efficacy, safety and pharmacodynamics of AK002 in CU subjects will be assessed through the following evaluations:

- 1) Safety and tolerability (adverse events, laboratory safety tests, etc.)
- 2) Disease activity scores (UAS7, [REDACTED])
- 3) [REDACTED]
- 4) Number of symptom-free days
- 5) Use of rescue medication (up to 3 sgAH tablets/day)
- 6) Effects on [REDACTED]
- 7) Number of [REDACTED]
- 8) [REDACTED]
- 9) Changes in trigger thresholds (in CINDU, including CholU)
- 10) Rate of [REDACTED] (UCT, [REDACTED]  
[REDACTED])
- 11) Serum levels of potential biomarkers of disease activity and treatment responses
- 12) Rates of relapse and sustained response (during post-treatment follow-up period)

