### 5.2 Other Endpoints

- 1) Safety of subjects treated with AK002: This includes physical examination, routine safety laboratory assessments, vital signs, electrocardiogram (ECG), urine safety, and adverse event reporting (Visits 2–10)
- 2) Change in disease activity as assessed by UAS7 and/or [REDACTED] (from Baseline to Visits 3, 5, 8, and 10)
- 3) Change in number of symptom-free days per week (patient diary-based CSU score; wheals, flares, itch, avoidance behavior) from Baseline to Visits 3, 5, 8, and 10
- 4) Change in [REDACTED] assessed by [REDACTED] from Baseline to Visits 3, 5, 8, and 10
- 5) Change in number of intake of rescue medication from Baseline to Visits 3, 5, 8, and 10
- 6) In case of [REDACTED], change in [REDACTED] from Visit 2 to Visit 3, 5, 8, and 10, as assessed by [REDACTED]
- 7) Change in number of [REDACTED] from Baseline to Visits 3, 5, 8, and 10
- 8) Change in [REDACTED] from Baseline to Visits 3, 5, 8, and 10
- 9) Changes in trigger threshold from Baseline to Visits 2, 3, 5, 8, and 10, as assessed by Pulse Controlled Ergometry Test (PCE) and FricTest®, as applicable
- 10) Rates of complete response, partial response, and non-response based on UCT, [REDACTED], trigger thresholds (where applicable), and QoL from Baseline to Visits 3, 5, 8, and 10
- 11) Serum levels at baseline and change from Baseline to Visits 3, 5, 8, and 10 of serum levels of potential biomarkers in AK002-treated subjects (e.g., tryptase, eosinophils, total IgE, basophils, eosinophil cationic protein)
- 12) Rates of AK002-treated subjects with relapse, rebound, sustained treatment effects at Visit 7

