### **13. Data Analysis**

This section outlines the statistical methods to be used for the analysis of the data from the study. A separate Statistical Analysis Plan (SAP), which will be completed and signed off prior to data base lock.

When the SAP differs from analyses described in the protocol, the SAP will take precedence.

Continuous variables will be summarized using number of non-missing observations, mean, standard deviation (SD), median, minimum, and maximum; categorical variables will be summarized using the frequency count and the percentage of subjects in each category.

Baseline for data analysis is defined as the last assessment prior to the first infusion of the study drug.

The primary summaries will be based on individual cohorts and the data from all 3 cohorts combined, wherever possible.

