## **13.5 Treatments (Study Drug, Concomitant Therapies, Compliance)**

Exposure to study drug will be summarized descriptively. The use of rescue medication is part of the efficacy assessment and will be reported there. Other concomitant therapy used both prior to and after start of study drug administration will be summarized. The WHO Drug Dictionary will be used for coding of medications.

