7.6 Treatments

7.6.1 Treatment Compliance and Extent of Exposure

Summaries of treatment compliance and exposure for AK002 and second generation of H1-antihistamine will be based on the safety population.

Duration of exposure is defined as the total number of days a subject is exposed to the study treatment. This will be calculated for each subject by taking the difference between the date of the last dose minus the date of the first dose, plus 1 (date of last dose – date of first dose +1).

Duration of Treatment exposure will be summarized using descriptive statistics (n, mean, standard deviation, median, minimum, and maximum).

Subjects will be tabulated with n (%) by the number of doses they received.

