11.2 Appendix B.1.1: Urticaria Patient Daily Diary for Patient with Cholinergic Urticaria

- 1) Did you do anything today that normally triggers symptoms?
 - No
 - Yes, with low intensity
 - Yes, with moderate intensity

- Yes, with high intensity
 - What exactly?

2) Did you have hives today?

- No
- Yes, with low intensity
- Yes, with moderate intensity
- Yes, with high intensity

3) Did you have any itching today?

- No
- Yes, with low intensity
- Yes, with moderate intensity
- Yes, with high intensity

4) How would you rate your symptoms overall today?

- Mild, easy to tolerate
- Moderate, quite noticeable, certain limitations
- Very intense, very noticeable, considerable limitations

5) Have you taken your daily tablet of antihistamines in the last 24 hours?

- No _____ Yes _____

6) Have you taken any rescue medication in the last 24 hours?

- No _____ Yes _____

How many

- 1 tablet, 2 tablet, 3 tablet

7) Have you taken any other medications besides your regular medications in the last 24 hours (for example, pain tablets, cortisone, ...)?

- No _____ Yes _____

How many

- 1, 2, ..., 10

Medication

- Drug taken: Today _____ Yesterday _____ Another Date _____
- Medication name _____ Indication _____ Dosage (mg) _____

How often during the study _____

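### Rescue medication is summarized only as the percent of subjects receiving any, which does not estimate the defined endpoint, a change from baseline in the number of intakes.

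*Protocol*

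**What the plan says.** Rescue use is a named secondary objective in Protocol 4.2: "Use of rescue medication (up to 3 sgAH tablets/day". The matching endpoint in Protocol 5.2, item 5 (repeated in the synopsis), is "Change in number of intake of rescue medication from Baseline to Visits 3, 5, 8, and 10".

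The data are collected daily. In SAP Appendix B.1.1, the diary for cholinergic urticaria, the item is "Have you taken any rescue medication in the last 24 hours", followed by a tablet count of "1 tablet, 2 tablet, 3 tablet". The diaries for urticaria factitia (B.1.2) and chronic spontaneous urticaria (B.1.3) ask for the same. Protocol Table 3 has the diary running from Visit 1, before the first dose.

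On analysis, Protocol 13.5 says: "The use of rescue medication is part of the efficacy assessment and will be reported there". The efficacy text it points to has one sentence on rescue, in 13.7.1: "Number and percent of subjects receiving rescue medication will be summarized". The sentence before it in 13.7.1 gives the other secondary variables a mean difference from Baseline at listed weeks; rescue is given neither.

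The SAP governs where the two differ: "When the SAP differs from analyses described in the protocol, the SAP will take precedence". Its readable endpoints (5.1 to 5.3) and efficacy analyses (7.7) contain no rescue item, although some exploratory items are redacted. SAP 3.7 records no changes to the protocol's analyses. SAP 7.6.1 says: "Summaries of treatment compliance and exposure for AK002 and second generation of H1-antihistamine will be based on the safety population". SAP 6.1 has diary data listed by subject.

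**The concern.** The endpoint is a within-subject change in a count. The stated analysis cuts that count at zero and does not compare it with baseline. With no window or visit named, a programmer could follow the sentence exactly and produce one cumulative percentage over the whole study, which cannot express a change at any level of use.

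This is a single-arm, open-label study with a patient-reported primary endpoint. Tablet counts help a reader judge whether a gain in UCT came with less antihistamine or with more. Protocol 6.1.2 allows rescue use to be adjusted during treatment, so movement in either direction is possible. A percent of users cannot tell a subject who cuts down from one who does not, or from one who takes more.

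**Working it through.** **1. Endpoint against analysis.** This step needs no assumption.

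| | Endpoint (Protocol 5.2, item 5) | Stated analysis (Protocol 13.7.1) |
|---|---|---|
| Quantity | number of intakes | any use, yes or no |
| Scale | 0 to 3 a day; 7 × 3 = 21 a week at most | 0 or 1 per subject |
| Comparison | change from Baseline | none |
| Time points | Visits 3, 5, 8 and 10 | none |
| Window | not given | not given |

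If every user goes from 2 tablets daily to 1, weekly tablets go from 14 to 7 while any use is 100% before and after, in any window. The same holds for a rise from 1 to 3 tablets daily (7 to 21 a week).

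**2. How insensitive is any use in other cases?** The documents give no rescue rate, so there is no figure to reproduce and all rates below are assumptions. With a mean of m tablets per day and a window of d days:

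- uniform (Poisson) use: P(any) = 1 − exp(−m·d)
- use varying between subjects (gamma, shape k): P(any) = 1 − (1 + m·d/k)^(−k)

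For example, with m = 0.2 and d = 7, 1 − exp(−1.4) = 75.3%. After halving, 1 − exp(−0.7) = 50.3%.

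| Assumed use, halved | Window | Any use before | Any use after |
|---|---|---|---|
| 2/day, uniform | 7 days | 100% | 99.9% |
| 1/day, uniform | 7 days | 99.9% | 97.0% |
| 0.5/day, uniform | 7 days | 97.0% | 82.6% |
| 0.2/day, uniform | 7 days | 75.3% | 50.3% |
| 0.2/day, uniform | 28 days | 99.6% | 93.9% |
| 2/day, uniform | 1 day | 86.5% | 63.2% |
| 1/day, k = 0.5 | 7 days | 74.2% | 64.6% |
| 1/day, half the users stop, the rest unchanged | 7 days | 99.9% | 50.0% |

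A ceiling appears when use is frequent and uniform or the window is long. It does not appear in general.

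**3. Chance of showing a halving.** This was simulated. Daily tablets are Binomial(3, p), with p from a Beta distribution of mean m/3 and precision 4. Either every subject's p is halved on average (with lognormal scatter, SD 0.6), or a random half of subjects stop. Any use is compared by exact McNemar and tablets by paired t, at the 5% level, in 7-day windows. The trial plans no tests, so these figures only indicate roughly how often a 95% CI for the change would exclude zero.

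| Pattern | n | Any use | Change in tablets |
|---|---|---|---|
| All reduce, 1.5 to 0.75/day | 12 | about 0% | 91% |
| All reduce, 1.5 to 0.75/day | 48 | 12% | 100% |
| All reduce, 0.5 to 0.25/day | 12 | 2% | 50% |
| All reduce, 0.5 to 0.25/day | 48 | 56% | 99% |
| Half stop, 1.5/day | 12 | 58% | 72% |
| Half stop, 1.0/day | 12 | 52% | 56% |
| Half stop, 1.5 or 1.0/day | 48 | 100% | 100% |

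Tablet counts are much better when subjects cut down. The two are close when the benefit comes from subjects stopping.

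**4. Precision of the replacement.** The 95% CI half-width is t(0.975, n−1) × SD/√n. For an assumed SD of change of 3 to 7 tablets per week, n = 12 gives 2.201 × 3/√12 = 1.9 up to 2.201 × 7/√12 = 4.4. At n = 48 the range is 0.9 to 2.0. Against a fall of 7 per week (2 to 1 tablet daily), that is informative even within one cohort of about 12.

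**The case against.** The strongest reply is that this is a descriptive pilot in which rescue use is item 5 of 12 other endpoints, and that number and percent is an ordinary summary. Shown by visit, it would reveal subjects who stop rescue. The tablet counts are not lost, because diary data are listed by subject. The SAP takes precedence in any case, so editing Protocol 13.7.1 alone would change no output.

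Much of this stands. The consequence is limited to description, and the SAP must carry the correction. But a listing is not an analysis. SAP 7.6.1 does not name rescue, and the only exposure measure it defines is a duration from first to last dose, not a number of tablets. The redacted SAP items cannot be counted for either side, so the claim is limited to the readable text.

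A reader might infer a stronger point: that antihistamine-refractory subjects will nearly all take rescue before and after treatment, so the percentage stays near 100% and cannot show a change. The documents do not support that. They give no rescue rate. UCT below 12 is an entry criterion and says nothing about use after treatment. Background antihistamine may be up to 4-fold (Protocol 8.2), so the need for tablets on top will vary. Under the assumed rates, any use falls from 75.3% to 50.3%, or from 99.9% to 50.0%, in cases that cannot be ruled out.

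**Conclusion.** The mismatch is established from the text alone: the stated summary does not estimate endpoint no. 5, and the readable SAP supplies nothing in its place. It misses reductions and increases in tablets among continuing users entirely.

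The size of the loss beyond that is conditional. If use is frequent and subjects cut down without stopping, the percentage hardly moves (99.9% to 97.0% at 1 tablet/day over 7 days). If use is sporadic, or if subjects stop, it moves clearly. All these rates, the simulation model and the SDs of change are assumptions. No test or decision in the trial depends on this endpoint, so the point is worth correcting but does not threaten the primary result.

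**What to change.** In Protocol 13.7.1 and in the SAP (an endpoint entry in section 5 and an analysis in 7.7), replace the any-use summary as the analysis of endpoint no. 5 with this:

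- Rescue tablets per week from the diary, calculated as 7 × the mean of the recorded days, in line with the SAP 6.4 rule for incomplete weeks.
- Change from the last pre-dose week to the week before each of Visits 3, 5, 8 and 10.
- Summaries by cohort, with mean, SD, median and a 95% CI for the mean change.
- Number and percent of subjects with any rescue use, by visit, kept as a descriptive line.

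The cost is a short text change and one more table; every diary version already holds the count. Tablet counts are skewed and bounded, which is why the median should stand beside the mean.
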